- Participant meets study definition of SLE, MS, RA, IBD, PsO/PsA, SOT, SCT, HM, ST, or HIV (see Appendix A: ICD-10-CM Codes for IC and Appendix B: Validated Coding Algorithms for IC conditions). Codes for IC conditions will be identified in the health plan claims of the DRN during the period 273 days prior to the pregnancy start date through the first trimester (98 days after the pregnancy start date). Diagnoses recorded through the first trimester will be included to account for women who may not have frequent visits prior to pregnancy and may have a more complete assessment of medical conditions during the first prenatal care visit.
- Participant has at least 273 days of continuous health plan enrollment with medical and drug benefits prior to the start of pregnancy through the delivery date, with gaps of up to 45 days in coverage being permitted. The 273-day pre-pregnancy period through the first trimester (a period of 98 days after the pregnancy start date) was chosen to allow identification of potential confounders of interest (Section 9.3.3). In Sentinel projects, gaps of 45 days or less in health plan enrolment are

214420 (EPI-ZOSTER-039 VS US DB) Protocol Amendment 2 Final

typically considered administrative gaps (and not lapses in health plan coverage) and ignored.

Pregnancies will be excluded from the study if the following exclusion criterion is met:

- Participant was exposed to a medication(s) that presents a known increased risk for fetal malformations (see Appendix C: Teratogenic and Fetotoxic Medications)
- Participant delivered an infant identified as having a chromosomal or genetic anomaly (Appendix D: Diagnosis Codes for Chromosomal or Genetic Anomalies
- Ectopic pregnancies, molar pregnancies or induced abortions.
- Multigestation (e.g., twin) pregnancies.

For analyses evaluating infant outcomes (Primary Objective and Secondary Objective 1), the cohort will include pregnancies resulting in live births for which the mother is linked to an infant. Each Sentinel Data Partner will be responsible for linking mothers to infants using all available local data resources. Algorithms linking mothers to infants will vary across Data Partners, generally looking for equivalent health plan subscriber numbers, delivery dates and dates of birth, and shared names and addresses. Sentinel Data Partners are able to link approximately 74% of their infants to their mothers [Sentinel Initiative, 2018].

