9.3.2. Outcomes (Amended 15 August 2022)

Outcomes to be evaluated include MCMs and additional infant/birth outcomes (preterm birth, SGA, LBW, NICU admission and neonatal death), complications of pregnancy (placental abruption, preeclampsia and eclampsia) and pregnancy outcomes (live birth, non-live birth [stillbirth and spontaneous abortion]). The primary outcome of this cohort study is MCMs of the infants.

As indicated in Section 9.2.1., the IC diagnoses of pregnant women and pregnancy outcomes will be identified from the health plan claims of the DRN containing ICD-10-CM Codes for IC conditions *and validated coding algorithms for IC conditions* during the period 273 days prior to the pregnancy start date through the first trimester (98 days after the pregnancy start date).

MCMs will be confirmed through chart review. Other outcomes will not be confirmed through chart review. Many of these ICD-10-CM algorithms for the secondary outcomes have not yet been validated. We will conduct a literature search prior to final analysis to determine potential validated algorithms for these secondary outcomes. Recent published studies provide evidence of the validity of ICD-10-based algorithms to identify adverse pregnancy outcomes. An international study reported moderate to high PPVs for ICD-10 codes for select secondary outcomes proposed in this study: 76.4% for LBW; 70.4% for SGA; 81.2% for preeclampsia [Watson, 2021].

Another recently published study in a US population reported higher PPVs for ICD-10-CM codes for preeclampsia and eclampsia (ranging from 89-100%) [Labgold, 2021]. In addition, an ongoing Sentinel COVID-19 pregnancy study, used ICD-10-CM codes to identify adverse pregnancy outcomes including preeclampsia/eclampsia, SGA and LBW. These algorithms were approved by the FDA team in the Hua 2021 study. Pregnancy episodes ending in a non-live birth pregnancy outcome will be identified using validated algorithms developed through Sentinel and non-Sentinel (e.g., VSD) projects [Andrade, 2021; Naleway, 2021].

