Appendix B. Validated coding algorithms for IC conditions (Amended 15 August 2022)

We will use the validated algorithms in the CBER Biologics Effectiveness and Safety (BEST) Initiative report [Saunders-Hastings, 2021] to identify IC conditions (solid organ transplant [SOT], stem cell transplant [SCT], hematological malignancy [HM], solid tumor [ST], human immunodeficiency virus [HIV]), as these are specific to each IC condition as well as valid and consistent with the typical approaches that are used in Sentinel. Algorithms for the IC conditions are described below:

- 1) HIV/AIDS: ≥ 2 claims for ANY HIV/AIDS diagnostic or procedural codes. a. This category is viewed as immunocompromised regardless of treatment status (treatment [RX]-independent)
- b. EXCLUDE cases where the most recent claim is MORE THAN 6 months prior to the index date.
- 2) Hematologic Malignancy and Related Conditions: ≥ 2 claims for ANY relevant diagnostic codes. a. This category is viewed as immunocompromised regardless of treatment status (RX-independent).
- b. EXCLUDE cases where the most recent claim is MORE THAN 6 months prior to the index date.
- 3) Solid Malignancy: ≥ 2 claims for ANY solid malignancy diagnostic codes AND one of: a. ≥ 2 claims for ANY codes for chemotherapy or radiation
- b. ≥ 2 claims for ANY codes for immune-modulating or immunosuppressant therapy
- c. EXCLUDE cases where the most recent claim is MORE THAN 6 months prior to the index date.

NOTE: Codes for brachytherapy may also be considered by users seeking to apply a more inclusive definition of radiation therapy. It is recommended that this category be ignored in regular applications of the algorithm, but it may be of value to those with a specific interest in brachytherapy.

- 4) Transplant and Related Conditions: ≥ 1 claims for ANY transplant or related condition diagnostic codes AND one of: a. ≥ 2 claims for ANY codes for chemotherapy or radiation
- b. ≥ 2 claims for ANY codes for immune-modulating or immunosuppressant therapy
- c. EXCLUDE cases where the most recent claim is MORE THAN 6 months prior to the index date.

NOTE: Codes for brachytherapy may also be considered by users seeking to apply a more inclusive definition of radiation therapy. It is recommended that this category be ignored in regular applications of the algorithm, but it may be of value to those with a specific interest in brachytherapy.

214420 (EPI-ZOSTER-039 VS US DB) Protocol Amendment 2 Final

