Appendix C. Teratogenic and Fetotoxic Medications (Amended 15 August 2022)

Women exposed to any of following potentially teratogenic or fetotoxic medications in the **273** days prior to and during pregnancy will be excluded from the study population. Exposures will be identified from NDC or HCPCS codes in the health plan claims data (outpatient pharmacy dispensing and encounter files).

Drug Class	Drug Name
Vitamin A Analog	Isotretinoin
Vitamin A Analog	Bexarotene
Vitamin A Analog	Acitretin
Prostaglandin Analog	Misoprostol
Antineoplastic	Methotrexate
Immunosuppressant	Mycophenolate Mofetil
Immunologic	Azathioprine
Immunologic	Thalidomide
Anticoagulant	Warfarin
Mood Stabilizer	Lithium
Antiarrhythmic	Amiodarone
Antiarrhythmic	Dronedarone
Anticonvulsant	Carbamazepine
Anticonvulsant	Fosphenytoin
Anticonvulsant	Mephobarbital
Anticonvulsant	Phenobarbital
Anticonvulsant	Phenytoin (phenytoin sodium)
Anticonvulsant	Primidone Primidone
Anticonvulsant	Topiramate
Anticonvulsant	Valproic Acid and derivatives (valproate sodium, divalproex)
Antirheumatic	Leflunomide
ACE-I	Benazepril
ACE-I	Captopril
ACE-I	Enalapril
ACE-I	Fosinopril
ACE-I	Lisinopril
ACE-I	Moexipril
ACE-I	Perindopril
ACE-I	Quinapril
ACE-I	Ramipril
ACE-I	Trandolapril
ARB	Candesartan
ARB	Eprosartan
ARB	Irbesartan
ARB	Losartan
ARB	Olmesartan
ARB	Telmisartan
ARB	Valsartan
Misc Antihypertensive	Aliskiren
SSRI	Paroxetine
Antiinfectives	Trimethoprim
Antiinfectives	Trimetrexate

ACE-I = Angiotensin-converting enzyme inhibitor; ARB = angiotensin II receptor blockers; SSRI = selective serotonin reuptake inhibitor

214420 (EPI-ZOSTER-039 VS US DB) Protocol Amendment 2 Final

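### Chemotherapy or radiation claims up to day 98 can admit a pregnancy, while Appendix C excludes only a few such treatments, so the malformation cohort can include pregnancies treated in the first trimester

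*Protocol*

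**What the plan says.** **Who gets in.** Under Appendix B, a solid-tumour or transplant pregnancy needs diagnosis claims plus one of two treatment routes: "≥ 2 claims for ANY codes for chemotherapy or radiation", or "≥ 2 claims for ANY codes for immune-modulating or immunosuppressant therapy". Haematologic malignancy needs two diagnosis claims and counts as immunocompromised with or without treatment.

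**When the claims may fall.** Section 9.2.1 reads the codes for immunocompromising (IC) conditions "during the period 273 days prior to the pregnancy start date through the first trimester (98 days after the pregnancy start date"). Section 9.3.2 places the codes "and validated coding algorithms for IC conditions" in the same window. Appendix B adds a recency rule, "EXCLUDE cases where the most recent claim is MORE THAN 6 months prior to the index date", without defining that date.

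**Who is removed.** Section 9.2.1 excludes a pregnancy if "Participant was exposed to a medication(s) that presents a known increased risk for fetal malformations", and refers to Appendix C for the drugs. Appendix C begins "Women exposed to any of following potentially teratogenic or fetotoxic medications in the" 273 days before and during pregnancy, then gives a list of named drugs found through NDC or HCPCS codes. One entry is classed as antineoplastic (methotrexate). Bexarotene, thalidomide, trimetrexate, mycophenolate mofetil, azathioprine and leflunomide also appear. There is no general chemotherapy entry and none for radiation.

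**What is balanced.** The propensity score variables named in Section 9.3.3 and Appendix I are demographics, calendar year, comorbidities, substance use, obesity and encounter counts. No cancer or transplant treatment is among them.

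**The concern.** The primary outcome is major congenital malformation (MCM). The inclusion algorithm can accept first-trimester chemotherapy or radiation as the evidence that admits a pregnancy, while the exclusion meant to take out malformation-risk medication reaches only a few of those treatments. If the unlisted treatments raise malformation risk, the cohort carries a cause of the outcome unrelated to the vaccine. The named propensity score variables would not balance it between groups.

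The outcome definition offers no second filter. Section 9.3.2.1.1 drops malformations that belong to syndromes of known cause, but ties this to Appendix D, which lists chromosomal and genetic codes. It also drops malformations secondary to other malformations. Chart review confirms the diagnosis. A treatment-related malformation would be counted as a case.

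**Working it through.** **1. The text, step by step.**
- A woman with two solid-tumour diagnosis claims and two chemotherapy or radiation claims, all between pregnancy start and day 98, satisfies Appendix B under the Section 9.2.1 and 9.3.2 window.
- If none of her drugs is named in Appendix C, the exclusion does not apply. If the treatment was radiation, it cannot apply.
- She stays in the MCM cohort when the infant is live-born, linked and otherwise eligible.
- If the undefined index date means pregnancy start, so that only earlier treatment claims count, the gap narrows but does not close. A woman admitted on earlier claims may continue treatment into pregnancy, and a haematologic malignancy qualifies without any treatment claim.

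**2. The plan's own figure.** Section 9.5 gives 711 exposed and 2133 unexposed (3% MCM, ratio 2.0, alpha 0.05, 90% power). The pooled two-sided formula returns exactly 711 if the 2.0 is entered as an odds ratio (0.06/1.03 = 5.825% v 3%). Entered as a risk ratio (6% v 3%), it needs 641, and 711/2133 has 92.5% power. The present point does not depend on that difference; 92.5% is the reference for step 4.

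**3. Null vaccine effect, unequal shares.** The 3% is from Section 9.5. Everything else is assumed, because Table 1 gives no prevalence for solid tumours, stem cell transplant or haematologic malignancy. Let a share f of comparators and 2f of the exposed have unlisted first-trimester chemotherapy or radiation, with MCM risk r:

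RR = [(1 − 2f) × 0.03 + 2f × r] / [(1 − f) × 0.03 + f × r]

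| f | r = 10% | r = 20% |
|---|---|---|
| 1% | 0.0314/0.0307 = 1.02 | 0.0334/0.0317 = 1.05 |
| 2% | 0.0328/0.0314 = 1.04 | 0.0368/0.0334 = 1.10 |
| 5% | 0.0370/0.0335 = 1.10 | 0.0470/0.0385 = 1.22 |

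With the same share in both groups, the numerator equals the denominator and RR = 1.00.

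**4. True ratio of 2, equal shares.** Assume 6% v 3% in the other pregnancies, and risk r in both groups among the treated, where the vaccine adds nothing:

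RR = [(1 − f) × 0.06 + f × r] / [(1 − f) × 0.03 + f × r]

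With r from 6% to 20% and 711/2133:
- f = 1%: RR 1.98 to 1.94, power 92% to 91%.
- f = 5%: 0.0600/0.0315 = 1.90 to 0.0670/0.0385 = 1.74, power 90% to 85%.
- f = 10%: RR 1.82 to 1.57, power 86% to 77%.

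**5. Scale.** At 3% MCM in both groups, the standard error of log RR is √(0.97/21.33 + 0.97/63.99) = 0.246. The 95% interval around RR = 1 is therefore about 0.62 to 1.62.

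**The case against.** The strongest reply has five parts.

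- **Matching.** The fallback plans in Section 9.2.1.3 match exactly on combined IC condition category. Since they relax the main plan, the main plan presumably does too. Pre-pregnancy encounter counts are a partial proxy for treatment intensity. This stands in part: a reader might infer that nothing balances these pregnancies, and that would be wrong. What matching leaves open is a difference between treated and untreated women, or in case mix, within a category.
- **Magnitude.** The doubled share is an assumption, and matching on category works against it. The top figure of 1.22 needs 10% of the exposed, about 71 of 711, to have had first-trimester chemotherapy or radiation. The smaller cases are modest beside a target of 2.0 and the interval in step 5. This stands.
- **Direction.** It is tempting to conclude that treated patients are vaccinated more often, so the bias runs upward. Women in both groups have an IC condition, and Section 7 expects exposure mainly through unintended pregnancy. The documents do not settle the direction.
- **Intent.** A reader might say the cohort contains fetuses the plan set out to exclude. The exclusion concerns medications and is defined by Appendix C. Radiation lies outside that wording, and nothing in the documents says that the unlisted agents carry a known risk. Only the mismatch can be shown.
- **Scope.** Chemotherapy or radiation is one of two routes and may lie entirely before pregnancy. For transplant, mycophenolate and azathioprine are listed, so part of the immunosuppressant route is already excluded.

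Section 9.9.1 also points to a bounding analysis in the SAP for unobserved confounders. These treatments are observable, in claims that Appendix B already needs, so bounding is a poor substitute for handling them directly.

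**Conclusion.** The concern holds as a mismatch between Appendix B and Appendix C. As written, the MCM cohort can include pregnancies with first-trimester chemotherapy or radiation, and no variable named in the protocol captures those treatments. The documents do not show that it will include many, or that the result is biased in a given direction.

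Under the stated assumptions the spurious risk ratio is 1.02-1.22 when the exposed have twice the comparators' share, and 1.00 when shares are equal. Equal shares are still not harmless: at 5% of both groups, a true ratio of 2 would be observed as 1.74-1.90, with power of 85-90% instead of 92.5%. The effect is probably small if such pregnancies are rare. The rule should nonetheless be settled before matching, because the claims are available and it defines the primary cohort. The length of the Appendix C look-back is a separate design choice and no part of this point.

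**What to change.** - Reconcile Section 9.2.1, Appendix B and Appendix C, and state whether pregnancies with chemotherapy or radiation after pregnancy start belong in the infant-outcome cohort.
- Define the index date in Appendix B, and say whether qualifying treatment claims may fall after pregnancy start.
- As an analysis-cohort rule, remove from the Primary Objective and Secondary Objective 1 cohort any pregnancy with a claim in the Appendix B chemotherapy or radiation code sets from pregnancy start through day 98. Earlier claims can still establish IC status. Apply the rule to both groups before matching, and to the feasibility count in Section 9.6.1.1, so that the 237 threshold refers to the same cohort.

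This concerns which pregnancies are analysed, not how patients are treated.

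The cost is protocol wording and one filter on code sets that Appendix B already calls for, plus the loss of a probably small number of cancer or transplant pregnancies. If a share f of the exposed were removed, keeping 711 would take 711/(1 − f): 719 at 1%, 749 at 5%, 790 at 10%. Without replacement, power for 6% v 3% would be 92.3%, 91.3% and 90.0%.

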Appendix C. Teratogenic and Fetotoxic Medications (Amended 15 August 2022)

Women exposed to any of following potentially teratogenic or fetotoxic medications in the **273** days prior to and during pregnancy will be excluded from the study population. Exposures will be identified from NDC or HCPCS codes in the health plan claims data (outpatient pharmacy dispensing and encounter files).

Drug Class	Drug Name
Vitamin A Analog	Isotretinoin
Vitamin A Analog	Bexarotene
Vitamin A Analog	Acitretin
Prostaglandin Analog	Misoprostol
Antineoplastic	Methotrexate
Immunosuppressant	Mycophenolate Mofetil
Immunologic	Azathioprine
Immunologic	Thalidomide
Anticoagulant	Warfarin
Mood Stabilizer	Lithium
Antiarrhythmic	Amiodarone
Antiarrhythmic	Dronedarone
Anticonvulsant	Carbamazepine
Anticonvulsant	Fosphenytoin
Anticonvulsant	Mephobarbital
Anticonvulsant	Phenobarbital
Anticonvulsant	Phenytoin (phenytoin sodium)
Anticonvulsant	Primidone Primidone
Anticonvulsant	Topiramate
Anticonvulsant	Valproic Acid and derivatives (valproate sodium, divalproex)
Antirheumatic	Leflunomide
ACE-I	Benazepril
ACE-I	Captopril
ACE-I	Enalapril
ACE-I	Fosinopril
ACE-I	Lisinopril
ACE-I	Moexipril
ACE-I	Perindopril
ACE-I	Quinapril
ACE-I	Ramipril
ACE-I	Trandolapril
ARB	Candesartan
ARB	Eprosartan
ARB	Irbesartan
ARB	Losartan
ARB	Olmesartan
ARB	Telmisartan
ARB	Valsartan
Misc Antihypertensive	Aliskiren
SSRI	Paroxetine
Antiinfectives	Trimethoprim
Antiinfectives	Trimetrexate

ACE-I = Angiotensin-converting enzyme inhibitor; ARB = angiotensin II receptor blockers; SSRI = selective serotonin reuptake inhibitor

214420 (EPI-ZOSTER-039 VS US DB) Protocol Amendment 2 Final

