8. RESEARCH QUESTION AND OBJECTIVES

The study will address the question of whether there is an increased risk of MCMs and additional infant/birth and pregnancy outcomes among women between 18 and 49 years of age with IC conditions exposed to HZ/su during pregnancy.

² Self-calculation

214420 (EPI-ZOSTER-039 VS US DB)
Protocol Amendment 2 Final

Primary objective:

1. Evaluate the prevalence of MCMs (as defined in Section 9.3.2.1.1) among live births from women with IC conditions exposed to HZ/su compared to those not exposed to HZ/su during pregnancy.

Secondary objectives:

- 1. Assess the prevalence of additional infant/birth outcomes (preterm birth, small for gestational age (SGA), low birthweight (LBW), neonatal intensive care unit (NICU) admission, neonatal death) among live births in women with IC conditions exposed to HZ/su versus those not exposed to HZ/su during pregnancy.
- 2. Assess the prevalence of pregnancy outcomes (livebirth, stillbirth and spontaneous abortion) and pregnancy complications (placental abruption, preeclampsia and eclampsia) among livebirth and non-livebirth pregnancies in women with IC conditions exposed to HZ/su versus those not exposed to HZ/su during pregnancy.

A feasibility assessment will be conducted (see Section 9.6.1.1). If the feasibility assessment determines that it is not possible to identify an adequate number of exposed live birth pregnancies among women with IC conditions for a cohort study, a descriptive analysis will be conducted. This analysis will describe the prevalence of infant and pregnancy outcomes among exposed and unexposed pregnancies with IC conditions, with no statistical comparisons performed (see Section 9.7.3).

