For analyses evaluating pregnancy outcomes (live birth, non-live births [stillbirth and spontaneous abortion]) and pregnancy complications (placental abruption, preeclampsia and eclampsia) (Secondary Objective 2), the cohort will include pregnancies resulting in a live birth and non-live birth (stillbirth), or spontaneous abortion.

For all analyses, the unit of analysis is a pregnancy episode.

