The LMP is widely accepted in electronic healthcare database safety studies as an estimate of the pregnancy start date and it is also in line with the European Medicines Agency (EMA) guidance. Numerous safety pregnancy studies have used LMP as an estimate of the pregnancy start date [Bateman, 2021; Hansen, 2016; Huybrechts, 2018; Kharbanda, 2021].

A published Sentinel study conducted within our Data Partners found \geq 90% agreement within 7 days between the claims data and medical charts for gestational age at stillbirth and 100% agreement within 30 days. Thus, misclassification of LMP based upon our algorithm to determine gestational age and LMP is expected to be minimal [Andrade, 2021].

Similar to the algorithm to determine live birth pregnancy episodes, ICD-10-CM and Current Procedural Terminology (CPT) codes will be used to identify non-live birth outcomes and calculate the length of the pregnancy episode, based upon published Sentinel [Andrade, 2021] and Vaccine Safety DataLink (VSD) studies [Naleway, 2021].

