Pregnancy outcomes will be compared between eligible pregnancies among women with IC conditions who were vaccinated with HZ/su during pregnancy and those who were not vaccinated with HZ/su during pregnancy. Univariate and multivariable statistical analyses will be performed as stated in the primary objective and secondary objective 1 (Section 9.7.2.1) for all outcomes. The prevalence of the pregnancy outcomes (live birth, stillbirth, and spontaneous abortion) and pregnancy complications (placental abruption, preeclampsia and eclampsia) and their 95% CIs will be calculated between the two groups of women. All analyses will be stratified by stage of pregnancy (pre-pregnancy, first trimester, second trimester, third trimester).

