Appendix H. Spontaneous Abortion and Stillbirth Diagnosis and Procedure Codes

Pregnancies ending in a spontaneous abortion or stillbirth will be identified with the following diagnosis and procedure codes using previously published algorithms [Andrade, 2021; Naleway, 2021].

Code	Code Category	Description	Pregnancy Outcome
002.1	ICD-10-CM	Missed abortion	Spontaneous abortion
O03.0	ICD-10-CM	Genital tract and pelvic infection following incomplete spontaneous abortion	Spontaneous abortion
O03.1	ICD-10-CM	Delayed or excessive hemorrhage following incomplete spontaneous abortion	Spontaneous abortion
O03.2	ICD-10-CM	Embolism following incomplete spontaneous abortion	Spontaneous abortion
O03.30	ICD-10-CM	Unspecified complication following incomplete spontaneous abortion	Spontaneous abortion
O03.31	ICD-10-CM	Shock following incomplete spontaneous abortion	Spontaneous abortion
O03.32	ICD-10-CM	Renal failure following incomplete spontaneous abortion	Spontaneous abortion
O03.33	ICD-10-CM	Metabolic disorder following incomplete spontaneous abortion	Spontaneous abortion
O03.34	ICD-10-CM	Damage to pelvic organs following incomplete spontaneous abortion	Spontaneous abortion
O03.35	ICD-10-CM	Other venous complications following incomplete spontaneous abortion	Spontaneous abortion
O03.36	ICD-10-CM	Cardiac arrest following incomplete spontaneous abortion	Spontaneous abortion
O03.37	ICD-10-CM	Sepsis following incomplete spontaneous abortion	Spontaneous abortion
O03.38	ICD-10-CM	Urinary tract infection following incomplete spontaneous abortion	Spontaneous abortion
O03.39	ICD-10-CM	Incomplete spontaneous abortion with other	Spontaneous abortion
O03.4	ICD-10-CM	complications Incomplete spontaneous abortion without complication	Spontaneous
O03.5	ICD-10-CM	Genital tract and pelvic infection following complete or unspecified spontaneous abortion	abortion Spontaneous abortion
O03.6	ICD-10-CM	Delayed or excessive hemorrhage following complete or unspecified spontaneous abortion	Spontaneous abortion
O03.7	ICD-10-CM	Embolism following complete or unspecified spontaneous abortion	Spontaneous abortion
O03.80	ICD-10-CM	Unspecified complication following complete or unspecified spontaneous abortion	Spontaneous abortion
O03.81	ICD-10-CM	Shock following complete or unspecified spontaneous abortion	Spontaneous abortion
O03.82	ICD-10-CM	Renal failure following complete or unspecified	Spontaneous

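### The misoprostol exclusion in Appendix C has no cut-off before the pregnancy outcome, so a claim made to manage a loss (or made at delivery) can remove a pregnancy from Secondary Objective 2 because of its outcome

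*Protocol*

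**What the plan says.** Protocol Section 9.2.1 lists as an exclusion: "Participant was exposed to a medication(s) that presents a known increased risk for fetal malformations", and refers to Appendix C for the drugs. It gives no window or exception of its own and does not limit the criterion to the live-birth cohort.

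Appendix C sets the window: women exposed to a listed drug in the 273 "days prior to and during pregnancy will be excluded from the study population". Misoprostol is listed as a prostaglandin analog, with no condition on indication or timing. The source is stated too: "Exposures will be identified from NDC or HCPCS codes in the health plan claims data (outpatient pharmacy dispensing and encounter files").

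The same study population feeds Secondary Objective 2. For that objective, Section 9.2.1 says "the cohort will include pregnancies resulting in a live birth and non-live birth (stillbirth), or spontaneous abortion". Section 8 states the aim: "Assess the prevalence of pregnancy outcomes (livebirth, stillbirth and spontaneous abortion) and pregnancy complications". Section 9.7.2.2 commits to reporting it: "The prevalence of the pregnancy outcomes (live birth, stillbirth, and spontaneous abortion") with 95% confidence intervals in the two groups. Appendix H counts "Missed abortion" (O02.1), the incomplete-abortion codes and several treatment procedure codes as spontaneous abortion.

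**The concern.** An eligibility rule in a cohort study should depend on what precedes the outcome. This one can be met by a claim that follows from the outcome. If a woman has a missed or incomplete abortion and misoprostol is dispensed or billed to manage it, the claim may be dated within the pregnancy episode. The pregnancy then leaves both the numerator and the denominator. A loss managed surgically stays in and may even be identified by its procedure code (for example 59812, 59820 or 59821). Whether a loss is counted can therefore depend on how it was treated.

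The prevalences of spontaneous abortion and stillbirth are a stated objective. If the feasibility count is not reached, Section 9.7.3 leaves prevalences with confidence intervals as the only product, and a stable risk ratio would then be no safeguard. Section 9.9.2 also presents better ascertainment of these two outcomes as a strength of the design.

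**Working it through.** The protocol states no figure on this point, so there is none to reproduce. The check has two parts: what the text implies, and an illustration of size under assumptions.

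**1. Which claims the rule catches.**

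- A claim dated before the assigned end of the episode is inside the window and excludes the pregnancy.
- A claim dated after that end is outside it.
- A same-day claim is not addressed.
- Section 9.2.1.1 says that diagnosis and procedure codes "will be used to identify non-live birth outcomes and calculate the length of the pregnancy episode", following published algorithms. It does not say which code fixes the end date when several are recorded, or how drug claims are ordered against it.
- Drug given in hospital without its own NDC or HCPCS code triggers nothing. Stillbirth is therefore likely to be affected less than spontaneous abortion.

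**2. Inputs for the illustration.** All are assumptions; none is in the protocol.

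- s: true prevalence of recorded loss, set at 15%
- m: share of losses removed by the rule, 10% to 30%
- k: share of live births removed by a claim at or near delivery, 0% to 30%

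**3. Only losses removed (k = 0).** Observed prevalence = s(1 − m) / (1 − s·m).

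- m = 10%: 0.135 / 0.985 = 13.7%
- m = 20%: 0.120 / 0.970 = 12.4%
- m = 30%: 0.105 / 0.955 = 11.0%

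**4. Live births removed as well.** Observed prevalence = s(1 − m) / [s(1 − m) + (1 − s)(1 − k)]. With s = 15% and m = 20%:

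- k = 0%: 0.120 / (0.120 + 0.850) = 12.4%
- k = 10%: 0.120 / (0.120 + 0.765) = 13.6%
- k = 20%: 0.120 / (0.120 + 0.680) = 15.0%
- k = 30%: 0.120 / (0.120 + 0.595) = 16.8%

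The direction therefore turns on whether m exceeds k. The prevalence is understated if m > k, unbiased if m = k and overstated if m < k.

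**5. Risk ratio (k = 0, s = 15% in the unexposed).**

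- Same m in both groups: a true ratio of 1.00 stays 1.00. A true 1.50 becomes 1.51 at m = 10% and 1.54 at m = 30%.
- m = 30% exposed, 20% unexposed, true ratio 1.00: 0.1099 / 0.1237 = 0.89
- m = 20% exposed, 30% unexposed, true ratio 1.00: 0.1237 / 0.1099 = 1.13

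**6. Events lost.** The protocol gives no size for Secondary Objective 2, so 711 exposed and 2133 unexposed are borrowed from the primary objective as an example. With a true risk of 5% in the unexposed and a ratio of 1.5, power is 69.1%. With m = 30% in both groups, the observed risks are 5.37% and 3.55%, and power at the same size is 56.5%.

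**The case against.** The strongest reply is that treatment for a diagnosed loss would ordinarily be billed on or after the diagnosis. If the episode ends at the first loss code, a later claim falls outside the window and nothing is removed. This limits the point. A reader might infer that every loss managed with misoprostol is removed, and the protocol does not support that. It does not rule the removal out either: the end-date rule is not stated, same-day claims are open, and a claim that precedes the code chosen as the end date is caught.

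A reader might also infer that loss prevalence is certainly understated in both groups. Step 4 shows that this needs m > k, and neither share is known. Nor is a biased comparison established. Both groups are women with immunocompromising conditions, matched within Data Partner on a propensity score that includes healthcare encounter counts, comorbidities and region. Different management of losses by vaccination status is possible, but nothing in the protocol indicates it.

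The protocol does concede under-capture of early losses and defers sensitivity analyses for selection bias to the SAP. However, the under-capture in Section 9.9.1 concerns losses without medical attendance, and the selection bias described there concerns restricting infant outcomes to live births. Neither covers attended, coded losses removed by a drug rule. The rule is an eligibility criterion fixed in the protocol, so it is not a detail that the SAP would be expected to supply.

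Finally, a blanket look-back exemption (for example 30 days before a loss code) could admit losses that the drug itself induced and that were coded as spontaneous. That objection stands and shapes the fix.

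**Conclusion.** The point holds in a limited form. As written, the rule has no cut-off before the outcome and applies to the Secondary Objective 2 cohort. A visible misoprostol claim made to manage a loss, dated on or before the assigned episode end, can remove that pregnancy because of its outcome. A claim at delivery can do the same to a live birth.

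The resulting distortion of loss prevalence is unknown in size, and its direction depends on whether more losses or more live births are removed, in relative terms. If no live births are removed, a true 15% would be seen as 13.7% to 11.0% for 10% to 30% of losses removed. The risk ratio is materially affected only if the shares differ by group: 0.89 or 1.13 instead of 1.00 under an assumed 30% against 20% split, depending on which group has the higher share. The effect is probably smaller for stillbirth.

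This rests on two things outside the protocol: that misoprostol is used to manage losses (general clinical knowledge), and the assumed values of s, m and k. The primary comparison of malformations contains no losses, so this mechanism for losses does not reach it. The change should be made because it is cheap and protects a stated objective.

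**What to change.** In Appendix C and Section 9.2.1, for the misoprostol eligibility rule, end the exclusion window before the first recorded loss code or the delivery encounter. Claims on or after that date then do not exclude the pregnancy, which also settles same-day claims. Keep the exclusion for earlier claims.

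Add a sensitivity analysis for Secondary Objective 2 that retains pregnancies whose only listed-drug claim is misoprostol shortly before a loss code, for example within 30 days. Report the number of pregnancies excluded by this rule, by exposure group and pregnancy outcome, so that the shares assumed above can be replaced by observed counts.

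The cost is a small amount of extra programming. The retained set may include some drug-induced losses coded as spontaneous, so the look-back belongs in the sensitivity analysis and not in the main rule.
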